3. INVESTIGATIONAL PLAN

3.1. Summary of Study Design

This is a dose-ranging, multicenter, randomized, double-blind, placebo-controlled study to evaluate the efficacy and safety of etrasimod 1 and 2 mg in Japanese participants with moderately to severely

active UC. The study consists of a 28-Day Screening Period, a 12-Week Induction Treatment Period, and a 4-Week Follow-Up Period ([Figure 1](#)). Eligible participants will be randomized (1:1:1 ratio) to receive either etrasimod (1 mg once daily), etrasimod (2 mg once daily), or matching placebo (once daily) in a double-blind fashion for 12 weeks. Randomization will be stratified by (a) naïve to biologic or JAK inhibitor therapy at study entry (yes or no), (b) baseline corticosteroid use (yes or no), and (c) baseline disease activity (modified Mayo score [MMS]: 4 to 6 or 7 to 9).

The target participant population will include those who have had an inadequate response to, loss of response to, or intolerance to the following:

[figure not shown]
- Conventional therapy, and are naïve to biologic or JAK inhibitor therapy
- Biologics or JAK inhibitors (participants in this category may have received prior conventional therapy)

Participant eligibility will be determined during a 4-Week (28-Day) Screening Period. Entry criteria will be based on confirmation of moderately to severely active UC, defined by an MMS of 4 to 9, which includes an ES \geq 2 and RB subscore \geq 1.

At the end of the 12-Week Induction Treatment Period, participants will undergo Week 12 efficacy and safety assessments and be evaluated for clinical response/remission. Participants will then have the option to enter an OLE study (Study APD334-303) following completion of Week 12 study procedures provided they meet all eligibility criteria for the OLE. Participants must complete Week 12 to be eligible for the OLE.

Participants who discontinue from the study and do not participate in the OLE study will have 2-Week and 4-Week Follow-Up visits after the last on-treatment visit/Early Termination (ET) visit ([Table 6](#)).

Figure 1: Study Design

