9.5. Follow-Up Period

For participants not participating in the OLE study, follow-up visits will be performed at 2 and 4 weeks after the last administration of study treatment as indicated in the Schedule of Assessments ([Table 6](#)).

If the ET or Study Completion visit is ≥ 2 weeks after the last administration of study treatment, the 2-Week Follow-Up visit is not required; however, the 4-Week Follow-Up visit should be scheduled and completed. If the ET or Study Completion visit is ≥ 4 weeks after the last administration of study treatment, the 4-Week Follow-Up visit is not required.

If the absolute peripheral lymphocyte count is not within normal limits at the 4-Week Follow-Up visit, participants should return for CBC with differential according to local standard of care (captured as subsequent Follow-Up visit or unscheduled visit).

All adverse events should be recorded for 30 days after last administration of study treatment (Section [9.9.8.2.2](#)).

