9.9.8.2.2. Recording Adverse Events

The adverse event reporting period for safety surveillance begins when the participant is initially included in the study (date of first signature of informed consent) and continues up to 30 days after the last administration of study treatment. If an adverse event is not resolved or stabilized by this time, the Sponsor in consultation with the Investigator will decide whether to continue to monitor the adverse event or closeout the event in the database if no further follow-up is necessary.

Investigators are not obligated to actively seek information on AEs or SAEs after the participant has concluded study participation. Any SAE suspected to be related to the study treatment must be reported whenever it occurs, irrespective of the time elapsed since the last administration of study treatment.

Investigators and study personnel will record all adverse events and SAEs whether received through an unsolicited report by a participant, elicited during participant questioning, discovered during physical examination, laboratory testing, and/or other means by recording them on the eCRF and/or SAE Form, as appropriate. The following information should be recorded on the adverse event eCRF:

- Description including onset and resolution dates
- Whether it met SAE criteria
- Severity
- Relationship to study treatment or other causality
- Outcome

For SAEs, events occurring secondary to the primary event should be captured and reported via the established safety reporting mechanism. .

The following should be considered when recording SAEs:

- Death is an outcome of an event. The event that resulted in the death should be recorded and reported on the eCRF.
- For hospitalizations, surgical, or diagnostic procedures, the illness leading to the surgical or diagnostic procedure should be recorded as the SAE, not the procedure itself. The

procedure should be captured in the narrative as part of the action taken in response to the illness.

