^w To be read by a blinded central reader. Proctosigmoidoscopy/colonoscopy should be performed prior to randomization to allow central reader review (may take approximately 5 to 12 days) and confirmation of eligibility ([Section 9.8.1.1](#)). If the ET visit is within 4 weeks of the last sigmoidoscopy and biopsy, these procedures do not need to be repeated.

^x Pharmacokinetic blood samples are to be collected predose, 4 hours (\pm 15 minutes) postdose on Week 0/Day 1 (PK sample to be collected after 12lead ECG), and predose (for trough level, within the 60minute period prior to dosing) on all other indicated days. A PK sample should be taken, if possible, at the time of any SAE or adverse event leading to study treatment discontinuation. In addition, for participants not enrolling into the APD334-303 study, a blood sample for PK should be drawn at the 2-Week and 4-Week Follow-Up visits. For all PK blood draws, the time of the last dose should be documented. For participants enrolling in the OLE at the Week 12 visit, the PK sample can be collected as part of the OLE.

^y Blood samples for biomarkers should be collected on the indicated days prior to the daily dosing as applicable.

^z Biomarkers will be collected at Week 12 but will not be collected at ET.

^{aa} All concomitant medications and procedures should be collected from Day 1 (predose) through the safety reporting period ([Section 6.7](#)).

^{bb} Study treatment should be dispensed at Week 12 if the participant continues treatment in APD334-303 OLE. Additionally, participants who consent and are eligible for the APD334-303 OLE study but do not enter the OLE on the same day as the Week 12 visit may also be dispensed study treatment.

^{cc} On days with scheduled study visits, participants should wait to take their study treatment until after blood draws for PK and after all pre-dose assessments and procedures have been completed.

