#### 18.1. Adverse Events

AEs will be coded using MedDRA (v24.1 or higher). The version used to code AEs will be displayed in the analyses. Treatment emergent adverse events (TEAEs) are defined as AEs that started or worsened in severity on or after the first dose of study treatment.

Refer to APPENDIX 2 for handling of partial dates for AEs for the purpose of assigning treatment-emergent flags. In the case where it is not possible to define an AE as treatment emergent or not, the AE will be classified as treatment emergent.

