#### Algorithm for Treatment Emergence of Adverse Events:

AE Start Date	AE Stop Date	Action
Known	Known, Partial or Missing	If AE start date < study treatment first dose date, then not TEAE  If AE start date ≥ study treatment first dose date, then TEAE
Partial, but known components show that it cannot be on or after date of first dose of study treatment	Known, Partial or Missing	Not TEAE
Partial, could be on or after date of first dose	Known	If AE stop date < study treatment first dose date, then not TEAE  If AE stop date ≥ study treatment first dose date, then TEAE
of study treatment OR Missing	Partial	Impute AE stop date as latest possible date (ie, last day of month if day unknown or 31st December if day and month are unknown), then:  If AE stop date < study treatment first dose date, then not TEAE  If AE stop date ≥ study treatment first dose date, then TEAE
	Missing	Assumed TEAE

Document: \quintiles.net\enterprise\Apps\sasdata\SASb\SAS\Arena\APD334\RZA28116\Biostatistics\Documenta

tion\SAP\503-Final SAP v2.0\APD334-203\_SAP\_Final v2.0-20231120\_clean.docx

Author: PPD Version Number: 2.0

Version Date: 20Nov2023

Template No.: CS\_TP\_BS016 Revision 7 Reference: CS\_WI\_BS005

Effective Date: 01Nov2021

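### The TEAE rule has no end date, so an adverse event recorded in this study after the first open-label etrasimod dose is tabulated under the participant's double-blind arm, placebo included

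*SAP*

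**What the plan says.** **TEAE rule.** SAP 18.1 covers events that "started or worsened in severity on or after the first dose of study treatment". The programming rule in SAP Appendix 2 for a known start date is "If AE start date ≥ study treatment first dose date, then TEAE". Both set a lower bound only.

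**Reporting period.** Protocol 9.9.8.2.2 starts adverse event reporting at consent and says that it "continues up to 30 days after the last administration of study treatment". Protocol 9.5 repeats this: "All adverse events should be recorded for 30 days after last administration of study treatment". Neither section exempts participants who go on to the extension.

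**Extension entry.** Protocol 3.1: "Participants will then have the option to enter an OLE study (Study APD334-303) following completion of Week 12 study procedures". No washout is stated. Footnote bb to Table 6 (Protocol Appendix 1) adds: "Study treatment should be dispensed at Week 12 if the participant continues treatment in APD334-303 OLE". Protocol 1.2 describes that extension as an evaluation of etrasimod.

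**Arm and denominator.** SAP 5.6 analyses the Safety Set by treatment received and has no rule for a switch at extension entry. In SAP 18.1.1, EAIR time runs to the first event for participants who have it, and to the last participation date for those who do not. SAP 10.1 counts the participants who continue to APD334-303, but no adverse event rule uses that information.

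**The concern.** A placebo participant who rolls over takes a first dose of etrasimod at extension entry. If that can happen on or soon after the Week 12 visit, up to 30 days of open-label dosing overlap the reporting period of this study. An event in that overlap, once recorded here, meets the TEAE definition and is shown under placebo. Participants from the 1 mg arm are affected in the same way if the extension dose differs from theirs; the documents do not give that dose.

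The terms most exposed are those tied to starting the drug. Protocol 1.3 names bradycardia at the first dose and AV block among the events reported with this drug class, and SAP 18.1.5 lists bradycardia and AV conduction delay as events of special interest. A drug event placed in the placebo column makes the arms look more alike. Protocol 1.3 says that the results are meant to support approval in Japan, so the by-arm safety tables matter even without formal tests.

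**Working it through.** The plan states no figure for this point, so the check applies the rules in sequence and then bounds the size.

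**1. Rule check: a placebo participant who completes Week 12 and enters the extension**
- An event starts after the first open-label dose and within 30 days of the last blinded dose.
- Protocol 9.9.8.2.2: it falls inside the reporting period.
- SAP 18.1 and Appendix 2: its start date is after the first dose, so it is a TEAE.
- SAP 5.6: the participant's arm is placebo, so the event is tabulated under placebo.
- SAP 18.1.1: the event enters the placebo EAIR numerator. A participant without the event stops contributing time at the last participation date. The SAP does not define that date; for extension entrants it is probably Week 12, because Protocol 1.3 equates study completion with the Week 12 assessments. Late cases can then count with no matching risk time from the others.

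**2. A further ambiguity**
Footnote bb calls the Week 12 supply for extension participants study treatment. The last administration of study treatment is therefore not clearly the last blinded dose, and the 30-day clock has no firm anchor.

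**3. Maximum share of days**
Dosing days: 12 × 7 = 84. Reporting after the last dose: 30. Share = 30 / (84 + 30) = 30/114 = 26.3%. This counts from first dose and assumes that open-label dosing starts at once.

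**4. One event in the placebo column**
1/32 = 3.1 points at the planned arm size. SAP 7 says the actual sample will be smaller, so one event would weigh more.

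**5. Illustration for any TEAE**
Assumptions: constant hazards over 84 days; the earlier Phase 2 rates in Protocol 3.2 (placebo 50.0%, 2 mg 56.0%); extension participants carry the 2 mg hazard; every event in the 30 days is recorded here.
- Placebo hazard = −ln(1 − 0.500)/84 = 0.00825 per day; 2 mg hazard = −ln(1 − 0.560)/84 = 0.00977 per day.
- Placebo incidence cut at the first open-label dose: 50.0%.
- With 30 more days at the 2 mg hazard: 1 − 0.500 × exp(−30 × 0.00977) = 62.7%, an excess of 12.7 points (about 4 of 32).
- With 30 more days at the placebo hazard: 1 − 0.500 × exp(−30 × 0.00825) = 61.0%.

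So about 11.0 of the 12.7 points are extra observation time and about 1.7 (62.7 − 61.0) come from the drug.

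| Share of placebo entering the extension | Excess in placebo any-TEAE incidence |
|---|---|
| 0% | 0 |
| 50% | 6.4 points |
| 80% | 10.2 points |
| 100% | 12.7 points |

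Extending the 2 mg arm by the same 30 days gives 1 − 0.440 × exp(−30 × 0.00977) = 67.2%. At full entry the 2 mg minus placebo difference is then 67.2 − 62.7 = 4.5 points, against 56.0 − 50.0 = 6.0 with the cut-off. General TEAE incidence is therefore not where the harm lies. Drug-specific first-dose terms are, because extra time on placebo would not produce them.

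**The case against.** The strongest reply is that few or no such events would reach this database. Protocol 1.3 treats the Week 12 assessments as study completion. Protocol 9.5 limits the 2-week and 4-week follow-up visits to participants who do not enter the extension, so the last scheduled adverse event assessment for the others is Week 12. Protocol 9.9.8.2.2 does not oblige investigators to seek events once participation has ended. Protocol 9.7 lets the Week 12 pharmacokinetic sample be collected as part of the extension, so some boundary data are already assigned there. This stands as a limit on how many events are captured. It does not remove a recorded event from the TEAE rule, and neither document states that this study's adverse event form closes at extension entry.

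Some of the supporting text is also thin. Footnote bb is about dispensing; it does not date the first open-label dose, and it also covers participants who do not enter on the same day. The sentence "Any SAE suspected to be related to the study treatment must be reported whenever it occurs" is a reporting duty for suspected related serious events and adds nothing to the 30-day overlap.

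On consequence, SAP 18 plans no statistical comparison of safety data unless otherwise specified, and the trial is stopping early (SAP 3.1 and 7). The minimum heart rate and change-from-predose summaries in SAP 18.5 are tied to Day 1 of this study and cannot be affected. All of that stands, and it confines the problem to the adverse event tables and the EAIR.

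A reader might infer that the placebo column will contain etrasimod events, or that 26% measures the bias. The documents support neither. The first depends on where the events are recorded, which is not stated; the second is a ceiling on calendar days.

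**Conclusion.** The gap is real and conditional. As written, an adverse event recorded in this study after the first open-label etrasimod dose is tabulated under the double-blind arm, placebo included, and enters the EAIR numerator, while risk time for participants without the event stops at their last participation date. The number of such events cannot be estimated from the documents: the extension entry rate, the extension dose and the receiving database are not given, and what is said about study completion points to few.

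The consequence worth guarding against is a bradycardia or AV conduction delay term appearing under placebo. At these arm sizes a single event is visible in the table. The any-TEAE illustration is a worst case that rests on constant hazards and full capture, and most of it is added follow-up time. Efficacy results do not depend on this point.

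**What to change.** - In SAP 18.1 and Appendix 2, end the TEAE window at the earlier of 30 days after the last double-blind dose and the first open-label dose.
- In SAP 18.1.1, end EAIR risk time at the same point, so that numerator and denominator cover the same period.
- State that, for this purpose, the last administration of study treatment means the last double-blind dose.
- List events after the cut-off separately, outside the by-arm tables.

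The cost is a few sentences in the SAP, one extra date (first open-label dose) in programming, and slightly fewer tabulated events. No data are lost, because later events are still listed. If the sponsor's practice already stops collection at extension entry, the change only writes that down.

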#### 18.1.1. All TEAEs

All TEAEs will be summarized by SOC and PT. This summary table and all other TEAE summaries by SOC and PT will be presented by descending frequency in the etrasimod total group. All AEs, regardless of treatment emergent status, will be included in an AE listing. Additionally, a listing of other AE details, as collected on the eCRF, will be presented.

Exposure-adjusted incidence rate (EAIR) of TEAEs will be summarized by SOC and PT. Exposure is defined as the sum of either time (year) from first dose to the onset of first such event for those who experienced this AE, or time (year) from first dose to last participation date in the study for those who did not experience this AE. The EAIR is calculated as the number of participants with the AE divided by the total exposure in subject-years.

#### 18.1.1.1. SEVERITY

Severity is classified as Grade 1: Mild, Grade 2: Moderate, Grade 3: Severe, Grade 4: Life threatening, Grade 5: Death related to AE, using the Common Terminology Criteria for Adverse Events, v5.0 (CTCAE v5.0).

Document: \quintiles.net\enterprise\Apps\sasdata\SASb\SAS\Arena\APD334\RZA28116\Biostatistics\Documenta

tion\SAP\503-Final SAP v2.0\APD334-203\_SAP\_Final v2.0-20231120\_clean.docx

Author: PPD Version Number: 2.0

Version Date: 20Nov2023

Template No.: CS\_TP\_BS016 Revision 7 Reference: CS\_WI\_BS005

Effective Date: 01Nov2021

Page 41 of 70

All TEAEs will be summarized by SOC, PT, and maximum severity, with SOC and PT presented by descending frequency of etrasimod total group. If a subject reports a TEAE more than once within a SOC/PT, the AE with the worst-case severity will be used in this summary.

TEAEs with a missing severity will be classified as Grade 3: Severe to study treatment for summary tabulation purpose only.

#### 18.1.1.2. RELATIONSHIP TO STUDY TREATMENT

Relationship is classified as "not related", "unlikely related", "probably related", or "related" by the Investigator.

All related TEAEs will be summarized by SOC and PT. A "related TEAE" for the purpose of this summary is defined as a TEAE with relationship to study treatment of "probably related" or "related".

All TEAEs will be summarized by SOC, PT, and highest relationship (as reported on the eCRF, not grouped), with SOC and PT presented by descending frequency of etrasimod total group. If a subject reports a TEAE more than once within a SOC/PT, the AE with the worst-case relationship to study treatment will be used in this summary.

TEAEs with a missing relationship to study treatment will be regarded as "Related" to study treatment for summary tabulation purpose only.

#### 18.1.2. TEAEs Leading to Discontinuation of Study Treatment

TEAEs leading to discontinuation of study treatment will be identified by action taken with study treatment being recorded as "Drug withdrawal" on the Adverse Events eCRF.

All TEAEs leading to discontinuation of study treatment will be summarized by SOC and PT. A listing of all TEAEs leading to discontinuation of study treatment will also be presented.

Liver-related AEs are defined by either SOC of hepatobiliary disorders or PT of alanine aminotransferase abnormal, alanine aminotransferase increased, aspartate aminotransferase abnormal, aspartate aminotransferase increased, hepatic enzyme abnormal, hepatic enzyme increased, liver function test abnormal, liver function test increased, transaminases abnormal, or transaminases increased.

#### 18.1.3. Serious and Non-Serious TEAEs

Serious adverse events (SAEs) are those events recorded as "Serious" on the Adverse Events eCRF.

Document: \quintiles.net\enterprise\Apps\sasdata\SASb\SAS\Arena\APD334\RZA28116\Biostatistics\Documenta

tion\SAP\503-Final SAP v2.0\APD334-203\_SAP\_Final v2.0-20231120\_clean.docx

Author: PPD Version Number: 2.0

Version Date: 20Nov2023

Template No.: CS\_TP\_BS016 Revision 7 Reference: CS\_WI\_BS005

Effective Date: 01Nov2021

Page 42 of 70

All serious TEAEs will be summarized by SOC and PT. If the seriousness is missing, the AE will be considered as "Serious" for summary tabulation purpose only. A serious TEAE listing will also be presented. All non-serious TEAEs will be summarized by SOC and PT.

#### 18.1.4. TEAEs Leading to Death

TEAEs leading to Death are those events which are recorded with an outcome as "Fatal" or AE Severity is equal to Grade 5 on the Adverse Events eCRF. All TEAEs leading to death will be listed.

#### 18.1.5. TEAEs of Special Interest

Categories of Targeted Medical Events (TMEs) and a list of preferred terms associated with these TME categories were developed based on the mechanism of action of etrasimod, prior experience with other agents acting via a similar mechanism, and disease specific clinical judgment. In addition, where standard testing has been implemented to screen for potential AESI (eg, electrocardiograms, spirometry, serum transaminases, etc.), the relevant data will be reviewed to identify potential cases of AESI that investigators may not have identified and to provide quantitative data for AESIs. The proposed candidate terms will be reviewed to identify which events reflect AESI.

Treatment-emergent AESIs will be summarized by category, subcategory, and PT by descending frequency by treatment group. Categories and subcategories of TEAEs of special interest are the following:

- Cardiovascular Events
  - Bradycardia
  - AV conduction delay
  - Hypertension
- Macular Edema
- Pulmonary Disorders
  - Airflow obstruction (forced expiratory volume in 1 second [FEV1], forced vital capacity [FVC])
  - Decrease gas exchange (diffusing capacity of the lungs for carbon monoxide [DLCO])
- Infections
  - Severe infections
  - Opportunistic infections (Narrow)

Document: \quintiles.net\enterprise\Apps\sasdata\SASb\SAS\Arena\APD334\RZA28116\Biostatistics\Documenta

tion\SAP\503-Final SAP v2.0\APD334-203 SAP Final v2.0-20231120 clean.docx

Author: PPD Version Number: 2.0

Version Date: 20Nov2023

Template No.: CS\_TP\_BS016 Revision 7 Reference: CS\_WI\_BS005

Effective Date: 01Nov2021

Page 43 of 70

- Herpes simplex and herpes zoster
- Liver Injury
  - Liver transaminases elevation
  - Bilirubin elevation
- Posterior Reversible Encephalopathy Syndrome (PRES)
- Malignancies

